5.4 Dose and Dosing Schedule

5.4.1 *Wilate* Dosage for PK Assessment in Paediatric Patients

For the PK assessment in paediatric patients (6–16 years), a single dose of 60 ± 10 IU/kg will be administered.

5.4.2 *Wilate* Dosage for Prophylactic Treatment

For prophylactic treatment, *Wilate* should be administered 2–3 times per week at a dose of 20–40 IU/kg BW for 12 months.

The prophylactic dose for each patient will be determined by the Principal Investigator based on each patient's clinical condition and at the following time points:

- At the Baseline IVR Visit (see Section 6.1.2) in adult patients (≥ 17 years)
In adult patients, the first prophylactic dose will be administered at the time of the baseline IVR assessment.
- At the Baseline PK Visit (see Section 6.1.4) in paediatric patients (6–16 years)
In paediatric patients, the first prophylactic dose will be administered after completion of the PK phase.

In case of unacceptably frequent spontaneous breakthrough BEs (i.e., more than 2 spontaneous BEs or 1 major spontaneous BE within a 30-day period), the dose of *Wilate* should be increased by approximately 5 IU/kg (depending on the entire content of the additional vials that need to be reconstituted). If, after a dose increase, patients still experience more than 2 spontaneous bleeding episodes, the dosing interval should be shortened from 2 times per week to 3 times per week.

5.4.3 *Wilate* Dose for the Treatment of Breakthrough BEs

The dose (and duration) of treatment of BEs will depend on the location and extent of bleeding and on the clinical condition of the patient.

Generally, 1 IU/kg BW VWF:Ac (VWF:RCo) and FVIII:C raises the plasma level by 1.5–2% of normal activity for the respective protein. Usually, about 20–50 IU *Wilate*/kg BW are necessary to achieve adequate haemostasis. This will raise the VWF:Ac (VWF:RCo) and

FVIII:C in the patients by approx. 30–100%.

The following should be used to guide dosing in the treatment of BEs:

Dose type	Minor haemorrhage*	Major haemorrhage
Loading dose	20–40 IU/kg	40–60 IU/kg
Maintenance dose	20–30 IU/kg every 12–24 hours	20–40 IU/kg every 12–24 hours
Therapeutic goal	Maintain VWF:Ac (VWF:RCo) and FVIII:C trough levels >30%	Maintain VWF:Ac (VWF:RCo) and FVIII:C trough levels >50%

*Menstrual bleeds of regular intensity (i.e., minor menstrual haemorrhage) will be considered normal and are not expected to require therapy unless deemed necessary by the investigator and/or the patient.

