In addition to the comparison of the patients' TABR during on-demand and prophylactic treatment, intra-individual comparisons with each patient's documented historical TABR will be performed. For this, descriptive statistics for historical TABR and TABR during prophylactic treatment and their intra-individual differences will be tabulated. Descriptive statistics will also be presented for the SABR.

Efficacy of Wilate in the Treatment of Breakthrough Bleedings

To assess the haemostatic efficacy of *Wilate* in the treatment of breakthrough BEs during prophylaxis, a frequency distribution of all treated BEs that were successfully treated will be presented overall and by severity, along with an exploratory 95% CI for the proportion of successfully treated BEs.

Pharmacokinetic Analysis

All PK analyses will be based on the PK set. The following PK parameters for will be analysed:

- Area under the curve (AUC) and AUC_{norm} (normalized for the administered dose)
- In vivo half-life (T_½)
- Maximum plasma concentration (C_{max})
- Time to reach maximum plasma concentration (T_{max})
- Mean residence time (MRT)
- Volume of distribution (Vd)
- Clearance (CL)
- Incremental in vivo recovery (IVR)

PK parameters will be computed for VWF:Ac (VWF:RCO) and FVIII:C. Both chromogenic (CHR) and one-stage (OS) assays, actual IMP potencies, and actual sampling times will be used in the calculations. PK parameters will be derived by non-compartmental methods.

The PK profiles of VWF:Ac and FVIII:C and the PK parameters derived from them will be summarized by descriptive statistics (including geometric means and standard deviations) as well as the presentation of concentration vs time plots (individual values and means).

Subgroup Analyses

Analyses of the primary endpoint assessing the efficacy of prophylactic treatment with *Wilate* and the secondary endpoint assessing the efficacy of *Wilate* in the treatment of breakthrough bleedings will be presented for the following subgroups:

- Age (6–11 years, ‘12–16 years,’ and ‘≥17 years’)
- Race (‘American Indian or Alaska Native,’ ‘Asian,’ ‘Black or African American,’ ‘Native Hawaiian or Other Pacific Islander,’ ‘White,’ ‘Other’)
- Geographical region (‘patients in the US,’ ‘patients outside the US’)
- Sex (‘female,’ ‘male’)

Analysis of PK parameters will be presented by age (‘6–11 years’ and ‘12–16 years’).

Efficacy of Wilate in Surgical Prophylaxis

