1.2 Secondary objective

The secondary objectives of this study are:

- Assess the incremental IVR of VWF:Ac and FVIII:C over time (at baseline, and at 1, 2, 3, 6, 9 and 12 months of treatment)
- Determine the pharmacokinetics (PK) of *Wilate* for VWF:Ac and FVIII:C in paediatric patients aged 6–16 years
- Assess the safety and tolerability of *Wilate* during prophylaxis
- Determine *Wilate* consumption data

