1.5 Planned sample size

Overall, 28 patients will be enrolled in this study, including at least 5 patients with VWD type 3, at least 5 patients aged 6–11 years, and at least 5 patients aged 12–16.

Assuming a mean total annualized bleeding rate (TABR) ratio (TABR_{pr} / TABR_{od}) of 0.25 with a correlation of 0.5 between the two treatment regimes, a coefficient of variation of 10 in on-demand treatment, and a coefficient of variation of 10 in prophylactic treatment, 25 patients will be needed to reject the null hypothesis

Statistical Analysis Plan	Version 6.0		Page 7 of 24
Sponsor	Octapharma	Protocol No	WIL-31

$$H_0: \text{mean}(\text{TABR}_{\text{pr}} / \text{TABR}_{\text{od}}) \geq 0.5$$

in favor of

$$H_1: \text{mean}(\text{TABR}_{\text{pr}} / \text{TABR}_{\text{od}}) < 0.5$$

with a type one error of 0.025 and power of 80% using a paired t-test for log-transformed data.

TABR_{pr} is defined as the total annual bleeding rate in the prophylactic treatment and TABR_{od} is defined as the total annual bleeding rate in the matching on-demand treatment period.

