3.6 Pharmacokinetic Set

The **pharmacokinetic (PK) set** will be a subset of the FAS containing all subjects with a pharmacokinetic assessment.

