3.8 Subgroup analyses

The analyses of the efficacy endpoints 'efficacy of prophylactic treatment' and 'efficacy in treatment of breakthrough BEs' will be presented in the following subgroups:

- Age groups ('6 to 11, 12 to 16 and >16 years').
- VWD type ('severe type 1', 'type 2' and 'type 3')
- Sex ('Female', 'Male')
- Race, according to CDISC Controlled Terminology (dependent on the number of subjects per race)

The safety analysis will be presented by the following subgroup:

- Age groups ('6 to 11, 12 to 16 and >16 years').

Statistical Analysis Plan	Version 6.0		Page 10 of 24
Sponsor	Octapharma	Protocol No	WIL-31

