4.8 Pharmacokinetics / Pharmacodynamics

For IVR assessments VWF:Ac (VWF:Rco and VWF:GP1bM) and FVIII:C (measured by both, the chromogenic (CHR) and one-stage assay (OS)) will be analyzed based on actual IMP potency.

Incremental IVR of *Wilate* over time (at baseline, 1, 2, 3, 6, 9 and at 12 months of treatment) will be analyzed in summary tables for each time point. For IVR analysis at baseline the IVRs derived from the paediatric PK profiles will also be included.

For children aged 6 to < 16 concentration versus time profiles will be obtained for VWF:Ac (VWF:Rco and VWF:GP1bM) and FVIII:C (OS and CHR) assays.

Calculation of PK parameters will be based on actual IMP potencies, on concentrations adjusted for residual pre-dose levels and actual time after end of infusion.

The following PK parameters will be derived from the adjusted concentration profiles.

:

Statistical Analysis Plan	Version 6.0		Page 18 of 24
Sponsor	Octapharma	Protocol No	WIL-31

- Area under the curve (AUC) and AUC normalized for the administered dose (AUC_{norm})
- In vivo half-life (T_½)
- Maximum plasma concentration (C_{max})
- Time to reach maximum plasma concentration (T_{max})
- Mean residence time (MRT)
- Volume of distribution (Vd)
- Clearance (CL)
- Incremental in vivo recovery (IVR)

The PK profiles and the PK parameters derived from them will be summarized by descriptive statistics (including geometric means and standard deviations, except for T_{max}) as well as the presentation of concentration vs. time plots. All derived PK parameters will be presented in by-patient displays.

PK profiles will additionally be presented graphically on original as well as semi-logarithmic scales as concentration-time curves, individually in spaghetti plots, and overall, showing the sample characteristic by time-point.

As PK data are only collected for children, the mentioned PK results will be presented in total and separately by age groups ('6 to <11' and '12 to <16' years) as well as by VWD type.

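### SAP 4.8 leaves 11- and 16-year-olds out of both PK age groups, and its PK assay list and Cmax/IVR basis conflict with other sections

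*SAP*

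**What the plan says.** **Age.** SAP 4.8 sets the profile population with "For children aged 6 to < 16 concentration versus time profiles will be obtained for VWF:Ac (VWF:Rco and VWF:GP1bM" (plus FVIII:C), and says results are "presented in total and separately by age groups ('6 to <11' and '12 to <16' years". Protocol 5.4.1 reads "For the PK assessment in paediatric patients (6–16 years), a single dose of" 60 ± 10 IU/kg. Protocol 9.2.2 says "Analysis of PK parameters will be presented by age" and names 6–11 and 12–16 years. Elsewhere the SAP follows the protocol. Its PK objective in 1.2 is "for VWF:Ac and FVIII:C in paediatric patients aged 6–16 years", 1.5 plans "at least 5 patients aged 6–11 years, and at least 5 patients aged 12–16", and the subgroups in 3.8 are "Age groups ('6 to 11, 12 to 16 and >16 years". The PK set in SAP 3.6 "will be a subset of the FAS containing all subjects with a pharmacokinetic assessment", with no age limit.

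**Assay.** SAP 4.8 lists both VWF:RCo and VWF:GP1bM for the concentration-time profiles. For PK, Protocol 6.1.4, 7.3, 9.2.2 and the PK row of Table 7, as well as SAP 4.7.2, name only VWF:RCo and FVIII:C. Protocol 3.1.2 lists GP1bM recovery at baseline, and 7.4.5.1 names GP1bM testing in plasma; neither gives an age limit.

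**Cmax and IVR.** SAP 4.8 derives every listed PK parameter, Cmax and IVR included, from profiles corrected for the level present before dosing. SAP 6.1 defines Cmax as the highest concentration actually measured after the infusion, and IVR as (Cmax − C0) × BW / D, where C0 is the last pre-dose concentration.

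**The concern.** Paediatric PK and IVR over time are both secondary endpoints, and the planned age groups are very small. Section 4.8 is the section a programmer would code from. Its two age intervals do not adjoin, so its literal limits give PK tables whose groups are not the protocol's, and SAP 2.2 does not declare this as a deviation.

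The assay list matters because SAP 4.8 also feeds recoveries from the paediatric PK profiles into the baseline IVR analysis. If GP1bM was not run on those samples, the GP1bM profiles cannot be produced, and children have no baseline GP1bM IVR from that source.

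The Cmax and IVR wording matters because two programmers, each following one section faithfully, could report different Cmax values from the same samples. Combining the two sections could also bias paediatric baseline IVR, which is then summarised together with the adult values.

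**Working it through.** The plan states no figure on this point to reproduce. The check compares the text and then sizes the possible effects.

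**1. Age limits.** There are 11 completed years of age from 6 to 16.

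- Protocol 9.2.2: 6–11 covers six ages and 12–16 covers five, so 6 + 5 = 11 and none is left out.
- SAP 4.8: 6 to <11 covers ages 6–10 (five) and 12 to <16 covers ages 12–15 (four), so 5 + 4 = 9. Ages 11 and 16 are in neither group.
- The SAP 4.8 profile range of 6 to <16 also excludes age 16. Age 11 stays in the total.

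Weight of one patient: 1/6 = 16.7% at the protocol minimum of 6 per group (Protocol 3.2), and 1/5 = 20% at the SAP 1.5 minimum of 5.

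Enrolled ages are not given. As an illustration only, assume that ages are uniform within each protocol group:

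- 6 per group: 6 × 5/6 = 5.0 and 6 × 4/5 = 4.8 patients are expected to remain. The chance that at least one patient is left out is 1 − (5/6)^6 × (4/5)^6 = 0.91.
- 5 per group: 4.2 and 4.0 are expected to remain, and the chance is 1 − (5/6)^5 × (4/5)^5 = 0.87.

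**2. Assays.** At the Baseline PK Visit, Protocol 6.1.4 schedules VWF:RCo and FVIII:C (OS and CHR) and no GP1bM sample. The paediatric Screening Visit (6.1.3) does include GP1bM, but no Wilate is given there, so that sample alone cannot yield a recovery. Against this, 3.1.2 and 7.4.5.1 name GP1bM at baseline and in plasma without excluding children. The documents therefore do not settle whether paediatric baseline GP1bM IVR exists.

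**3. Cmax and IVR.** Let d be the dose in IU/kg, so that D = d × BW, and let r be the rise per IU/kg. Protocol 5.4.3 gives r = 1.5–2% per IU/kg, and Protocol 5.4.1 gives d = 60, range 50–70. Assume that the adjustment subtracts C0 from the peak; the SAP does not give its form.

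- Measured Cmax = C0 + r × d. Adjusted Cmax = r × d. The reported Cmax differs by C0: with r = 1.5, d = 60 and C0 = 10, it is 100 against 90.
- Measured Cmax with measured C0: IVR = (C0 + r × d − C0)/d = r.
- Adjusted Cmax with no second subtraction: IVR = r × d/d = r. The result is the same.
- Adjusted Cmax with raw C0: IVR = (r × d − C0)/d = r − C0/d, a relative shortfall of C0/(r × d).

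Shortfall under the mixed reading only:

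- C0 = 0: 0%.
- C0 = 10 IU/dL: 10/120 = 8.3% to 10/90 = 11.1% at 60 IU/kg; 10/140 = 7.1% to 10/75 = 13.3% over 50–70 IU/kg.
- C0 = 30 IU/dL: 30/120 = 25.0% to 30/90 = 33.3% at 60 IU/kg; 30/140 = 21.4% to 30/75 = 40.0% over 50–70 IU/kg.

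Both non-zero C0 values are assumptions. The 30 IU/dL figure is the VWF:RCo entry limit for type 1 in Protocol 4.1.2, and the documents give no pre-dose distribution.

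**The case against.** The strongest reply is that these are drafting slips with little consequence. The limits <11 and <16 look like slips for <12 and <17, and a slip would not be declared in SAP 2.2. The PK set has no age limit, and results are also shown in total and by patient, so no one's data need be lost. SAP 3.8 concerns efficacy and safety subgroups rather than PK, so the conflict inside the SAP rests mainly on the 6–16 range in 1.2. If GP1bM was run on the PK samples, 4.8 merely adds a descriptive assay; if not, some tables are empty. Either consistent reading of IVR corrects once, and SAP 6.1 as written is correct on its own. The revision history shows that version 6.0 introduced the adjustment, so the 6.1 definition of Cmax may simply not have been updated.

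Much of this is fair. A slip is the likely explanation for the age limits, the double subtraction is permitted rather than required, and the largest IVR percentages come from the least certain part of the point. A C0 of exactly 30 IU/dL lies just outside the type 1 criterion, although that criterion sets no limit for type 2 or for FVIII:C.

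The mismatches themselves remain. The age limits are an operative rule, and a program follows what is written. Nothing in the SAP says whether 4.8 or 6.1 governs Cmax; SAP section 4 even refers the reader to a section 8.1 for the PK definitions, while the SAP ends at section 7.

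**Conclusion.** The point holds, with different certainty for its parts.

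- **Age limits: definite.** Two of the 11 ages are in no PK age group, and one of them is also outside the stated profile range. The number of patients affected is unknown and could be 0; each would remove 17–20% of a minimum-size group.
- **Assay list: a definite conflict.** Its practical effect depends on which assays were run, which the documents do not show.
- **Cmax: a definite conflict.** The reported value differs by the pre-dose adjustment according to the section followed.
- **IVR: conditional.** There is no error if either section is applied consistently. The calculated shortfalls arise only if an adjusted Cmax is combined with a raw C0, and they rest on assumed C0 values and the protocol's expected recovery.

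Everything affected is a descriptive secondary output. The correction should be made, but nothing here bears on the primary TABR test.

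**What to change.** 1. In SAP 4.8, define the PK population as patients aged 6–16 years and the age groups as 6–11 and 12–16 years, as in Protocol 9.2.2.
2. Reconcile the PK assay list in 4.8 with SAP 4.7.2 and Protocol 3.1.2, 6.1.4, 7.3 and 7.4.5.1. Remove VWF:GP1bM from the PK profiles if it was not assayed in the PK samples, and state which patients contribute to baseline GP1bM IVR.
3. In SAP 4.8 and 6.1, state that IVR uses measured Cmax and measured C0, so that the pre-dose level is removed once. Say whether the reported Cmax is measured or adjusted. A consistently adjusted IVR would also correct once; what matters is that a single rule is written down.

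The cost is SAP wording and one check of which assays were run on the paediatric PK samples. No new data are needed.

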4.9 Safety

All safety analyses will be based on the SAF population.

The safety and tolerability of Wilate will be assessed by monitoring adverse events (AEs) throughout the study. The analysis of safety will include the occurrence of AEs, the results of the safety laboratory tests, immunogenicity measurements and the occurrence of parvovirus B19 seroconversions.

4.9.1 Adverse events

Adverse events (AEs) will be coded by the Data Management of the CRO according to the Medical Dictionary for Regulatory Activities (MedDRA). Coding will be agreed upon with the Sponsor before database lock (cf. DMP).

All adverse events occurring during study will be listed in appendix 16.2 of the report.

The analysis will include only treatment-emergent adverse events (TEAEs), i.e. all documented AEs that started or worsened after the start of the first IMP infusion. It is assumed that for each increase in intensity of an AE a new entry of the AE will be done by the investigator; hence such cases will be analyzed like different phases of the same AE.

A descriptive analysis will be performed. Incidences will be presented by SOC and incidences of PT within primary SOC sorted according to the Internationally Agreed Order.

Multiple counts within a PT or SOC (repeated or different included terms or changes in descriptors) will be counted only once for the calculation of incidences.

Statistical Analysis Plan	Version 6.0		Page 19 of 24
Sponsor	Octapharma	Protocol No	WIL-31

Global incidences will be calculated for:

- All TEAE irrespective of the causality assessment
- Related TEAEs ('Probably' or 'Possible'), i.e. Adverse Drug reactions (ADRs)
- TEAEs by worst severity
- Serious TEAEs

A listing of "special cases" containing subject identification, age, sex, AE descriptors, start and end of treatment will be prepared for the following types of TEAEs:

- Serious adverse events (SAE)
- Adverse events which led to death
- Adverse events which led to discontinuation

Serious non-treatment emergent AEs will be listed separately.

4.9.2 Vital Signs

Vital signs parameters (systolic/diastolic blood pressure, pulse, body weight, respiratory rates, body temperature) will be assessed at screening, IVR baseline, after 1, 2, 3, 6 and 9 months IVR visit, and at study completion visit. Body weight will also be documented within 12 hours before start of surgery.

Descriptive analyses of values will be performed and changes from baseline (before IMP administration) will be analyzed for vital signs parameters at visits.

4.9.3 Safety Laboratory variables

The analysis of the safety lab values for

Hematology: RBCs, WBCs, haemoglobin, haematocrit, and platelet count

Clinical chemistry: Total bilirubin, ALT, AST, blood urea nitrogen, serum creatinine

recorded during visits (screening and study completion visit), urine pregnancy test results recorded during visits (screening, 3, 6 and 12 months) and at surgery will be purely descriptive and presented as summary tables or listings.

Time profiles of the safety laboratory parameters will be analyzed by presenting sampling statistics for the values as well as their difference to baseline (before IMP administration) at each time point. Additionally, frequency tables for values outside the normal ranges will be presented.

Similarly, time profiles of VWF- and FVIII-inhibitor testing results will be analyzed by presenting sampling statistics for the values as well as frequency tables for positive findings, along with 95% Pearson-Clopper CIs.

To assess the viral safety of *Wilate* incidences of parvovirus B19 seroconversions between IVR baseline and end of study will be estimated along with 95% Pearson-Clopper CIs.

4.9.4 Other safety variables

Other safety parameters (e.g., changes in physical examination findings) will be analyzed by summary tables or listings. All abnormal findings from the physical examination will be listed.

Statistical Analysis Plan	Version 6.0		Page 20 of 24
Sponsor	Octapharma	Protocol No	WIL-31

The analysis of the safety parameters recorded during surgery (lab values) will be purely descriptive and presented as summary tables or listings.

4.10 Other variables

Not applicable.

4.11 Interim analyses

Not applicable.

5 QUALITY CONTROL

The SAP was reviewed by the trial statistician (TS) before signature. Particularly the TS has checked the consistency of the described methods and outputs with the actual version of the study protocol. In addition, a sponsor representative has reviewed the SAP before final approval.

Log files of all SAS® programs used in the analysis will be checked for errors, warnings and suspicious notes by the statistical programmer. All findings will be either eliminated or commented upon. The final version of each program will be stored along with its log file in the electronic archive.

All programs will be validated by the program author or an independent statistical programmer depending on the requested validation level selected in the List of TLFs.

The agreement of the program outputs with the SAP, their consistency and plausibility will be checked by the TS. Moreover, the TS will review the outputs regarding completeness, readability and comprehensibility.

The described process is associated with the 'normal' level of program validation. Additional levels of quality control can be specified in the List of TLFs (see Appendix, 1) for individual outputs.

Statistical Analysis Plan	Version 6.0		Page 21 of 24
Sponsor	Octapharma	Protocol No	WIL-31

6 DERIVATIONS AND TRANSFORMATIONS

6.1 Formulas for derived variables

Variable	Description
Durations between two dates	Later date minus earlier date plus 1, expressed in days. (Remark: Duration will be 1, if both dates are the same.)
On-Demand period (days)	(Date of study completion – date of screening + 1) - Surgery period. Applicable for historical data from WIL-29
Surgery Period _{od} (days)	Formula for surgery period under on-demand treatment correspond to formula for surgery period under prophylactic treatment but replacing “IMP” by “VCP (von Willebrand factor containing product)”. Applicable for historical data from WIL-29
Prophylactic treatment phase (days)	((last date of IMP + 2 OR completion date, whatever occurred earlier) – first date of prophylactic IMP +1) – Surgery period.
Surgery Period (days)	Individual surgery period: last date of IMP in context of surgery (reason = “Prophylaxis after surgery” or “Surgery”) – date of surgery + 1 or 1 day (i.e. day of surgery) in case surgery not treated/no treatment information available. Surgery period: Sum of individual surgery periods per subject. All BEs at day of surgery with onset after start of surgery and all BEs occurring under post-operative prophylaxis (reason = “Prophylaxis after surgery”) will be excluded from the calculation of ABRs
Annualized Bleeding Rates On-Demand (ABR _{od})	Formulas for ABR under on-demand treatment correspond to formulas for ABR under prophylactic treatment but replacing “prophylactic treatment phase” by “on-demand period”. Individual annualized bleeding rates under on-demand period will be taken from calculated rates in study WIL-29 for all subjects along with total number of bleedings
Total Annualized Bleeding Rate Prophylaxis (TABR _{pr})	Number of bleedings under prophylactic treatment phase (except menstrual bleedings) / (prophylactic treatment phase /365.25)
Spontaneous Annualized Bleeding Rate Prophylaxis (SABR _{pr})	Number of spontaneous bleedings under prophylactic treatment phase /(prophylactic treatment phase/365.25)
Traumatic Annualized Bleeding Rate Prophylaxis (TRABR _{pr})	Number of traumatic bleedings under prophylactic treatment phase / (prophylactic treatment phase/365.25)
Heavy Menstrual Annualized Bleeding Rate Prophylaxis (HMABR _{pr})	Heavy Menstrual Annualized Bleeding Rate: Number of heavy menstrual bleedings under prophylactic treatment phase / (prophylactic treatment phase/365.25)

Statistical Analysis Plan	Version 6.0		Page 22 of 24
Sponsor	Octapharma	Protocol No	WIL-31

Variable	Description
ED	Exposure day = each calendar day the subject received IMP
C ₀	Last concentration before IMP administration
C _{max}	Maximum plasma concentration. Maximal measured concentration after end of IMP infusion (peak concentration)
T _{max}	Time to reach C _{max} (Timing starts at end of injection)
T _{1/2}	$\text{In vivo half-life } T_{1/2} = \frac{\ln(2)}{K}$ 
K = elimination rate constant, determined as the slope of the regression line) using linear regression on the terminal phase of the logarithm of the concentration

AUC	Area under the curve from baseline to infinity $AUC = \sum \left(\frac{(C_n + C_{n+1})}{2} \cdot \Delta t \right) + \frac{C_{last}}{K}$ 
(C_{last} is the last available measurement)

AUC _{norm}	AUC normalized for the administered dose
AUMC	Area under the moment curve (from baseline to infinity) $AUMC = \sum \left(\frac{(t_n \cdot C_n + t_{n+1} C_{n+1})}{2} \cdot \Delta t \right) + \frac{C_{last}}{K^2} + \frac{t_{last} \cdot C_{last}}{K}$
MRT	Mean residence time $MRT = \frac{AUMC}{AUC}$
CL	Clearance $CL = \frac{D}{AUC}$ where D is the actual dose administered
Vd	Volume of distribution at steady state: $Vd = CL \cdot MRT$
Incremental in vivo recovery (IVR)	$IVR = \frac{(C_{max} - C_0) \cdot BW}{D}$ 
where BW = body weight in kg and D = dose of IMP

Hemostatic success (in treatment of bleeding episodes and surgeries)	Success: efficacy rating is 'excellent' or 'good' Non-Success: efficacy rating 'moderate' or 'none' or 'missing'
Duplicate test results	If more than one blood sample for the same time point and test has been taken and two valid results are available/have been captured into the database, the mean of the values will be used in analysis

Statistical Analysis Plan	Version 6.0		Page 23 of 24
Sponsor	Octapharma	Protocol No	WIL-31

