Concomitant medications	7.1.2	x	x	x	x	x	x	x	x	x	x	x	x	x	x

FLOW CHART FOR PK ASSESSMENT AND PROPHYLACTIC TREATMENT (PAEDIATRIC PATIENTS)—Continued

IVR = in vivo recovery, VWD = von Willebrand disease, VWF:Ac = VWF activity, GP1b = glycoprotein 1b, FVIII = factor VIII, FVIII:C = factor VIII procoagulant activity, OS = one-stage assay, CHR = chromogenic assay, PBAC = Pictorial Blood Loss Assessment Chart, PROMIS = Patient-Reported Outcomes Measurement System, SF-36v2 = 36-Item Short Form Health Survey (version 2), SF-10 = 10-Item Short Form Health Survey

LEGEND TO THE FLOW CHART FOR PK ASSESSMENT AND PROPHYLACTIC TREATMENT (PAEDIATRIC PATIENTS)

- * **COMPLIANCE CALL:** monthly telephone calls to take place ± 1 week to review compliance with completing diary, obtaining PBAC (for female patients of child-bearing potential), adherence with infusion regimen, AEs, and concomitant medications (see **Section 6.1.11**)
- (•) If inhibitor development is suspected
- [1] Before injection
- [2] Within 60 min before and 60 ± 5 min after injection
- [3] Blood samples for PK assessment to be taken within 60 min before injection and 60 ± 5 min, 3 h (± 30 min), 9 ± 1 h, 24 ± 2 h, 48 ± 2 h, and 72 ± 2 h after injection (central laboratory)
- [4] Before injection, if sample at the Baseline PK Visit was negative, or if it was equivocal on both original and re-testing
- [5] Before starting any other visit assessment
- [6] Target joint(s) are defined as having 3 or more spontaneous bleeding episodes into a single joint within 6 consecutive months preceding the Baseline Visit or the Study Completion Visit.
- [7] In female patients of child-bearing potential

FLOW CHART OF ASSESSMENTS FOR SURGICAL PROPHYLAXIS

Assessment	For details, see Section	Within 12 hours before start	Within 3 hours before start	Surgery		POP day 1	Any POP day	End of POP period
				Intra- operatively	End [1]			
Body weight		x						
Type of surgery	7.2.4	x						
Location of surgery	7.2.4	x						
Severity of surgery	7.2.4	x						
Expected duration of surgery	7.2.4	x						
Actual duration of surgery	7.2.4				x			
Expected average/maximum blood loss during surgery	7.2.4	x						
Actual blood loss and transfusions during surgery	7.2.4				x			
Administration of Wilate	7.2.1		x	(x)	(x)	(x)	(x)	(x)
FVIII:C plasma levels	7.2.4		# L	(#) L	(#) L	(#) [2] L	(#) L	(#) L
VWF:Ac plasma levels	7.4.5		# L	(#) L	(#) L	(#) [2] L	(#) L	(#) L
Routine safety laboratory	7.4.5	x				(x)	(x)	(x)

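### SAP 6.1 uses straight-line trapezoids across gaps of up to 24 h on a declining intravenous profile, leaves the end-of-infusion concentration undefined, and lets a zero or negative adjusted value serve as C_last

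*SAP*

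**What the plan says.** The formula table in SAP 6.1 gives AUC as "Area under the curve from baseline to infinity": the sum of mean adjacent concentrations times the interval length, plus C_last/K. AUMC applies the same linear rule to t·C, with the matching tail. MRT is AUMC/AUC, CL is dose/AUC and Vd is CL·MRT.

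Three supporting definitions matter:

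- C_last "is the last available measurement". No condition on sign or quantification is attached.
- K is found "using linear regression on the terminal phase of the logarithm of the concentration". The number of points is not given.
- C0 is the "Last concentration before IMP administration". No concentration at the end of infusion is defined.

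SAP 4.8 bases the parameters "on concentrations adjusted for residual pre-dose levels and actual time after end of infusion". Protocol 3.1.2 and footnote [3] of the paediatric flow chart schedule samples before the dose and at 1, 3, 9, 24, 48 and 72 h. SAP 4 names non-compartmental software and refers to a section 8.1 for definitions, but the SAP has no such section. SAP 3.7 leaves exclusion of invalid samples or profiles to the data review meeting.

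**The concern.** After an intravenous dose the concentration falls roughly exponentially. A straight line between two points on such a curve always lies above it, and the excess grows with the gap. Half of the six post-dose points are reached across gaps of 15, 24 and 24 h.

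The first hour is open: the programmer must choose a value at time 0 or leave the interval out, and the choice changes the results.

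Once the pre-dose level has been adjusted out, a late sample can be zero or negative. The tail term is then zero or negative, and that sample has no logarithm for the regression that gives K.

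AUC, dose-normalised AUC, CL, MRT and Vd all depend on this formula, and paediatric PK is a named secondary endpoint. The error does not shrink with more children, and it varies with half-life.

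**Working it through.** The documents state no PK result, so there is no figure of the plan's own to reproduce.

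**Inputs.** The formulas are those of SAP 6.1 and the times those of Protocol 3.1.2. The half-lives are assumptions, since the documents give none. The decline is noise-free, C(t) = 100·exp(-Kt), with the true K, so only the integration rule is tested. Exact values are AUC = 100/K and AUMC = 100/K².

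**Worked case, half-life 12 h.** K = ln 2/12 = 0.05776. Exact AUC = 1731.2; exact AUMC = 29,971.7. Concentrations at the six times are 94.39, 84.09, 59.46, 25.00, 6.25 and 1.5625.

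- Linear AUC, 1 to 72 h: 178.5 + 430.6 + 633.5 + 375.0 + 93.8 = 1711.3.
- The exact area there is (94.39 - 1.5625)/K = 1607.0, so straight lines add 104.3. The 24-48 h interval alone adds 375.0 - (25.00 - 6.25)/K = 375.0 - 324.6 = 50.4.
- AUC tail: 1.5625/K = 27.1.
- Linear AUMC, 1 to 72 h: 26,972.5. Its tail: 1.5625/K² + 72·1.5625/K = 2415.9.

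Three readings of the first hour are possible:

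- True C(0) = 100: adds (100 + 94.39)/2 = 97.2, so AUC = 1835.6.
- Adjusted pre-dose zero at t = 0: adds 94.39/2 = 47.2, so AUC = 1785.6.
- Sum starts at 1 h: adds nothing, so AUC = 1738.4.

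In the first two readings AUMC is the same, 26,972.5 + 47.2 + 2415.9 = 29,435.6, because t·C is zero at t = 0 whatever C is. In the third it is 29,388.4.

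Since Vd = dose·AUMC/AUC², the AUC error enters twice. With C(0) true, the AUMC ratio is 29,435.6/29,971.7 = 0.982 and the AUC ratio is 1835.6/1731.2 = 1.060. The Vd ratio is 0.982/1.060² = 0.874, that is -12.6%.

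**Error by half-life (AUC / MRT / Vd, %).**

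| Half-life | True C(0) | Zero at t = 0 | Start at 1 h |
|---|---|---|---|
| 8 h | +9.5 / -8.1 / -16.0 | +5.1 / -4.3 / -8.9 | +1.1 / -0.9 / -2.0 |
| 12 h | +6.0 / -7.4 / -12.6 | +3.1 / -4.8 / -7.7 | +0.4 / -2.3 / -2.8 |
| 16 h | +4.0 / -6.0 / -9.6 | +1.8 / -4.0 / -5.8 | -0.3 / -2.1 / -1.9 |
| 24 h | +2.0 / -3.7 / -5.6 | +0.5 / -2.3 / -2.8 | -0.9 / -1.0 / -0.1 |

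**Replacement rule.** Log trapezoids on declining intervals, with C(0) back-extrapolated from 1 h and 3 h, give 0.0% error on all these curves. On three assumed bi-exponential curves they give AUC +0.9% to +1.4% and Vd -1.4% to -1.9%. The linear rule with a zero start gives AUC +0.9% to +3.0% and Vd -3.5% to -7.0% on the same three curves.

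**Sign of the last value.** Protocol 5.4.3 expects a rise of 1.5-2% per IU/kg. At the midpoint, 60 IU/kg gives 60·1.75 = 105 IU/dL. Assume a 12 h half-life, subtraction of the pre-dose value C0, and independent assay error with CV 5-10%. The true adjusted 72 h value is 105/2⁶ = 1.64, and SD = CV·√(C0² + (C0 + 1.64)²). The probability of a value at or below zero is Φ(-1.64/SD).

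- C0 = 2 IU/dL: 0%.
- C0 = 10: SD 0.77 to 1.53, giving 2% to 14%.
- C0 = 20: SD 1.47 to 2.95, giving 13% to 29%.

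At a 16 h half-life and C0 = 20 the range is 0% to 7%. A C0 of 20 is compatible with eligibility, because type 1 patients qualify with VWF:RCo below 30 IU/dL.

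**The case against.** The strongest reply is that the SAP never places a zero at time 0. It says only that AUC runs from baseline and that concentrations are adjusted. C0 appears in a formula only for IVR, and the pre-dose sample precedes the injection while time runs from the end of infusion. The software might back-extrapolate, or the sum might start at 1 h. This stands: a reader might infer that the plan starts the profile at zero, but the text supports only that the starting value is undefined.

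A reader might also infer that a zero start and the straight lines compound in MRT and Vd. They do not. A zero start lowers AUC and leaves AUMC alone, so it raises MRT and Vd and offsets part of the error: at 12 h, Vd is -12.6% with the true C(0) and -7.7% with zero.

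Nor is the extrapolation term biased in itself. With the right K it is correct, and at 12 h it is only 27.1/1731.2 = 1.6% of AUC. The weakness is the missing rule for non-positive values, and how often it bites depends heavily on the assumed pre-dose level.

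Finally, PK is summarised descriptively, and the protocol asks for as few as four evaluable children per age group. The data review meeting can exclude invalid profiles, and SAP 5 has the trial statistician check output for plausibility. These are real but partial safeguards: neither is a numerical rule, and neither changes the trapezoid.

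**Conclusion.** The point holds as a modest, correctable defect in a stated formula. Over assumed half-lives of 8 to 24 h, the straight-line rule with the true starting value overstates AUC by 9.5% to 2.0% and understates MRT by 8.1% to 3.7% and Vd by 16.0% to 5.6%. With a zero at the start, AUC is +5.1% to +0.5%, MRT runs from -4.3% to -2.3% with its largest error near -4.8% at 12 h, and Vd is -8.9% to -2.8%. Starting at 1 h leaves Vd at -2.8% to -0.1%. At 8 h the unstated choice therefore moves Vd by 14 percentage points (-16.0% against -2.0%).

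The missing condition on C_last is a separate gap. Its frequency, 0% to 29% at a 12 h half-life, rests on assumed pre-dose levels and assay CV.

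A reader might infer that the comparison of ages 6-11 with 12-16 is distorted. That would require the groups to differ in half-life, and the documents say nothing on this. Cmax and IVR do not use these formulas. Half-life does not use the trapezoid, but it depends on K and so on the rule for non-positive values. The primary test is unaffected.

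**What to change.** Amend SAP 6.1 in one step, because correcting the start alone can enlarge the error (at 12 h, Vd would go from -7.7% with a zero start to -12.6%):

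1. Use linear-up/log-down trapezoids for AUC and AUMC.
2. Define the end-of-infusion concentration by log-linear back-extrapolation from the 1 h and 3 h samples. Carry the 1 h value back if that slope is not negative.
3. Define C_last and t_last as the last adjusted concentration that is positive and quantifiable, and exclude later values from the regression for K.
4. Correct the SAP 4 reference to section 8.1.

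The cost is SAP wording and re-programmed software settings, with no new samples. Reported values will shift slightly; results under the linear rule can be kept as a side table.
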